## Design

**Table 1: Trial design**

Trial design, including number of arms		Two-arm prospective, individually randomised controlled trial
Unit of randomisation		Individual participant and practitioner
Stratification variables (if applicable)		Service (youth justice/edge of care/ youth development/early help/ children’s services), Sex (male/ female), age group (<15 years, >= 15 years)
Primary outcome	variable	Quantity of self-reported delinquent acts at 6 months 
	measure (instrument, scale, source)	Self-Reported Delinquency Scale (SRDS)
Secondary outcome(s)	variable(s)	Participant Quantity of self-reported delinquent acts at 12 months

---

 The requirement of the funding means a report needs to be available by September 2025, this means the primary outcome is the 6-month version of the SRDS. As some interventions take longer than 6-months to deliver a second report using SRDS at month 12 will also be produced later.

		
Self-report behaviour and personality attributes (overall behaviour, emotional symptoms, conduct problems, hyperactivity, peer relationships, prosocial behaviour, externalising behaviours, internalising behaviours), psychological health, wellbeing, family cohesion, police involvement, school exclusions, suspensions, managed moves and employment status. At 6 and 12 months.
 
Staff Attitudes and perceptions towards trauma informed care, wellbeing, absence, turnover at 6 and 12 months

	
measure(s) (instrument, scale, source)
	
Participants
 
Self-Reported Delinquency Scale (SRDS), Strengths and Difficulties Questionnaire (SDQ), General Health Questionnaire (GHQ12), Short Warwick Edinburgh Mental Wellbeing Scale (SWEMWBS), Brief Family Relationship Scale (BFRS), Client Service Receipt Inventory (CSRI)
 
Staff
 
Attitudes related to Trauma Informed Care (ARTIC), Short Warwick Edinburgh Mental Wellbeing Scale (SWEMWBS), Staff records.

Baseline for primary outcome	variable	Quantity of self-reported delinquent acts in previous six months
	measure (instrument, scale, source)	Self-Reported Delinquency Scale (SRDS)
Baseline for secondary outcome	variable	
Participant
 
Number of offences in the 6-months prior to baseline.

		
Self-report behaviour and personality attributes (overall behaviour, emotional symptoms, conduct problems, hyperactivity, peer relationships, prosocial behaviour, externalising behaviours, internalising behaviours) derived from the Strengths and Difficulties Questionnaire, psychological health, wellbeing, family relationships at baseline.
 
Police involvement, school exclusions and suspensions, employment status over the past 6 months at baseline.
 
Staff Attitudes and perceptions towards trauma informed care and wellbeing at baseline.
 
Days' absence and turnover over the past 6 months at baseline.

	
measure (instrument, scale, source)
	
Participants
 
Self-Report delinquency Scale (SRDS), Strengths and Difficulties Questionnaire (SDQ), General Health Questionnaire (GHQ12), Short Warwick Edinburgh Mental Wellbeing Scale (SWEMWBS), Brief Family Relationship Scale (BFRS), Client Service Receipt Inventory (CSRI),
 
Staff
 
Attitudes related to Trauma Informed Care (ARTIC), Short Warwick Edinburgh Mental Wellbeing Scale (SWEMWBS), Staff records.

## Randomisation

There are two levels to the study randomisation. Level one involves staff being allocated to be trained in RBT or remain delivering BAU. This allocation is done for all staff, after baseline staff data collection, and is conducted by an on-line independent secure randomisation service, Sealed Envelope Ltd. Staff in Youth Development Services will be youth workers and mentors who work directly with young people, in Early Help they will be staff who support

young people and families, in Edge of Care Services and Children's Services staff will predominantly be social workers and social work assistants and in Youth Justice Services they will be professionals who work with young people to reduce reoffending. Staff already trained in RBT in the YOT will be ineligible. Consent will be sought from all eligible staff prior to randomisation. As allocations are done at the same time and because we want to maximise balance across the groups on key parameters, we will employ minimisation for the allocation of staff. Our aim will be to maximise balance in terms of service (youth justice, edge of care, youth development, early help, children's services) and sex (male or female). Provision has been made to conduct a second wave of staff randomisation and TRM training if there is a high turnover of staff throughout the trial – a high turnover is one that exceeds 30%.

Level two allocation involves the randomisation of young people to RBT or BAU. This will be conducted by research staff, using a secure, on-line randomisation service (Sealed Envelope Ltd). after informed consent has been taken and the baseline assessment completed and before any trauma screening has been conducted. The allocation will involve an equal probability of receiving RBT or BAU and will employ random permuted blocks of variable size (4, 6 or 8) with a random block seeded throughout. Randomisation will be conducted by research staff using a secure, independent randomisation service, Sealed Envelope Ltd. Randomisation will be stratified by service (youth justice, edge of care, youth development, early help, children's services), sex (male, female), and age group (<15 years, 15 years or more). Stratification variables have been chosen to ensure allocation is balanced across services, sex, and age as some workers specialise in working with older or younger males and females. A full quality assurance AUDIT trail will be kept of all allocations and research staff will not be able to see future allocations. The allocated group will be relayed back to delivery staff in the services who will decide which staff member, matching their allocated intervention or control group, a young person should be assigned to.

It is not possible to blind young people or staff to their allocated group although follow-up at months 6 and 12 will be conducted by researchers blind to allocation. Follow-up questionnaires are completed by participants and are the same for both groups, the questionnaires collect no details on what group the participant was allocated to.

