## **Intervention**

The intervention, RBT, involves a model of practice that aims to avoid stigmatising and criminalisation of young people through the identification and formulation of a sequence of

interventions that respond to the childhood trauma experienced by the young people. Greater detail on the theoretical framework and the intervention approach is available here: <https://www.trmacademy.com/#theModel> and the hypothesised theory of change is articulated in figure 1. The intervention builds on work already delivered in youth justice services in Bridgend over the past 18 months, to include a population of young people in other services: Edge of Care, Children's Services, Youth Development, and Early Help – who may be starting to display challenging behaviour as a response to their trauma.

Practitioners are randomly allocated to receive training or not using a secure on-line randomisation service employing a minimisation algorithm which means staff are allocated to ensure balance between service and specialisation. 50% are allocated to RBT training and 50% continuing with BAU. The initial training is delivered to 35-40 staff members over 3-days by specialist trainers from the Trauma Recovery Model Academy. Trainers are experienced practitioners; social workers, clinical psychologists and youth workers who have developed and delivered the RBT intervention for many years across several different services working with young people. Training aids practitioners to understand the impact of prior trauma on the young person's behaviour, the development of strategies to reduce the behavioural consequences of trauma, building relationships and communication, the principles of case management and how to employ evidence-based interventions to promote positive development, and ensuring trauma histories are embedded in the case management process.

Up to ten senior members of staff, consisting of managers for each service and those currently responsible for core assessment of need on referral, will receive an additional two-day training with the aim of becoming trauma leads and champions within their departments. These staff will receive monthly mentoring throughout the project and shadowing from other similar services in Wales. These trauma leads will take responsibility for the core assessment of need, case formulation meetings and embedding trauma informed practice within services.

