Secondary outcomes will be assessed in a similar way by establishing diagnostic plots to identify the most appropriate regression approach; logistic for dichotomous outcomes, ordinal for ordered categorical outcomes, linear for continuous outcomes and fractional for proportions. Stratification factors and baseline covariates will be included within the model.

If the missing data exceeds 5%, sensitivity analyses will be performed using a pattern mixture approach and multiple imputation to compare the sensitivity of conclusions to varying assumptions about the missing data, particularly whether data is missing at random (MAR) or missing not at random (MNAR). This allows for an assessment of both random and systemic bias. Results based on complete data analysis, MAR and MNAR will be presented to explore the influence of missing data on outcomes observed.

We will conduct a Complier Average Causal Effects (CACE) analysis using an instrumental variable framework to explore the impact of compliance on the primary outcomes at different levels of compliance, both fidelity to the steps involved in each tier and quintiles of compliance. CACE weights the analysis by the ITT treatment effect by the proportion of compliance, this allows the estimation of unbiased treatment effects and maintains the allocation in the analysis.

Objective 3: For staff we will explore the differences between the groups in terms of overall wellbeing, perceptions of working in a trauma informed manner and confidence in working with young people who have experienced adverse childhood experiences derived from the SWEMWBS and ARTIC questionnaire at months 6 and 12 using linear regression adjusted for baseline score and service. Staff turnover and proportion absence will be assessed in a similar manner using fractional regression.

Objective 5: Stepwise regression analysis will be performed to model the relationship between pre-randomisation factors and demographics, on observed outcomes at 6 months.

Interaction terms with allocation arm will be included in the analysis, and a significance level of 0.1 will be used to determine which factors are to be included in the regression model. Pre-randomisation factors will include sex, age, ethnicity, IMD, family cohesion, adverse childhood experiences assessed by the service, and process measures, staff perceptions, staff confidence, and therapeutic alliance. The allocated arm will be included in this analysis as an interaction term.

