The efficacy trial design is a mixed method, two level, individually randomised controlled trial of a trauma informed intervention, Trauma Recovery Model Relationship Building Together (RBT), versus business as usual (BAU) for adolescents and young adults served by Bridgend Youth Services (youth justice, edge of care, youth development and early help). There are two levels to the study randomisation. Level one involves selecting staff to be trained in RBT. This allocation is done for all staff, after baseline staff data collection, and is conducted by an on-line independent secure randomisation service, Sealed Envelope Ltd. Consent will be sought from all eligible staff prior to randomisation. As allocations are done at the same time and because we want to maximise balance across the groups on key parameters, we will employ minimisation for the allocation of staff. Our aim will be to maximise balance in terms of service (youth justice, edge of care, children's services, youth development, and early help) and speciality (specialised staff versus generic staff). Provision has been made to conduct a second wave of staff randomisation and TRM training if there is a high turnover of staff throughout the trial – a high turnover is one that exceeds 30%.

Level two allocation involves the randomisation of young people to RBT or BAU. This will be conducted by research staff, using a secure, on-line randomisation service (Sealed Envelope Ltd). after informed consent has been taken and the baseline assessment completed and before any trauma screening has been conducted. The allocation will involve an equal probability of receiving RBT or BAU and will employ random permuted blocks of variable size (4, 6 or 8) with a random block seeded throughout. Randomisation will be stratified by service (youth justice, edge of care, children's services, youth development and early help), sex (male, female), and age group (<15 years, 15 years or more). Stratification variables have been chosen to ensure allocation is balanced across services, sex, and age as some workers specialise in working with older or younger males and females.

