$$SRDS12_{i,j} = \alpha + \beta_1(\text{allocation})_{i,j} + \beta_2(SRDS0)_{i,j} + \beta_3(\text{sex})_{i,j} + \beta_4(\text{age})_{i,j} + \beta_5(\text{service})_j + \varepsilon_i$$

Where for participant i within service j ; $SRDS12$ is the 12-month SRDS score, $allocation$ is the allocated group, $SRDS0$ is the baseline SRDS score, sex is the participant sex, age the age group, $service$ the service level dummy variables to adjust for fixed effects and ε_i the individual level error.

Other secondary outcome analysis at months 6 and 12, will be based on the ITT dataset. All secondary outcomes are continuous in nature, and after the examination of diagnostic plots to establish that the underlying assumptions for a linear analysis of covariance are met, they will be using an approach similar to that used in the primary outcome analysis (eq.3).

$$OUT_{i,j} = \alpha + \beta_1(\text{allocation})_{i,j} + \beta_2(OUT0)_{i,j} + \beta_3(\text{sex})_{i,j} + \beta_4(\text{age})_{i,j} + \beta_5(\text{service})_j + \varepsilon_i$$

Where for participant i within service j ; OUT is the 6 or 12-month outcome, $allocation$ is the allocated group, $OUT0$ is the baseline outcome value, sex is the participant sex, age the age group, $service$ the service level dummy variables to adjust for fixed effects and ε_i the individual level error.

Staff outcomes (ARTIC score, wellbeing and rates of absence) will be analysed using an analysis of covariance adjusted for baseline values and stratification factors: service and specialist versus generic.

Outcomes will be presented for each allocated group as means and the associated estimates of precision, 95% confidence intervals.

Subgroup analyses

To maintain power in the analysis we will avoid analysing sub-groups and instead use the whole sample for latent class analysis to explore for the emergence of clusters of participants who may have a differential response to the RBT intervention. Latent class approaches allow for clusters to emerge from the data rather than being pre-specified. In addition to the baseline variables being collected we will also include measures of ethnicity, material deprivation and therapeutic alliance assessed at month 6 using the short revised therapeutic alliance scale for children (TASC-r; (Shirk and Saiz, 1992)).

Further analyses

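### The staff minimisation factors are stated two ways (service and sex, or service and specialism), and the Protocol's staff model leaves out one of the factors on either reading

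*Protocol*

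**What the plan says.** **Allocation rule for staff (level one)**

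- Protocol, Randomisation: minimisation aims at balance on service and sex. The list of factors ends "early help, children's services) and sex (male or female".
- Protocol, Intervention: "staff are allocated to ensure balance between service and specialisation".
- SAP, Introduction: service "and speciality (specialised staff versus generic staff". The level 1 entry in the SAP's Design overview table names the same two factors.
- SAP, Imbalance at baseline: staff balance is examined by service and specialism.

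**Model for staff outcomes**

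- Protocol, Analysis, Objective 3: ARTIC and SWEMWBS are analysed "using linear regression adjusted for baseline score and service". Turnover and absence are handled similarly by fractional regression.
- SAP, Secondary outcome analysis: ARTIC, wellbeing and absence are analysed by analysis of covariance "adjusted for baseline values and stratification factors: service and specialist versus generic".

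Both documents allow a second wave of staff randomisation if turnover exceeds 30%.

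**The concern.** A trial report has to state how its practitioners were allocated, and the staff analysis should condition on the factors used to allocate them. At present two rules and two models are written down. The conflict lies inside the Protocol as well as between the Protocol and the SAP, so giving one document precedence does not fully settle it.

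What is at stake is the precision of the objective 3 comparisons. Minimisation removes part of the chance variation between arms on the factors it uses. A model that leaves such a factor out still counts that variation in its standard error, so the interval is wider than the design warrants. The rule may also be needed again, since a second wave would have to be run on a single stated set of factors.

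**Working it through.** **1. The two readings side by side**

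| | If service and sex were used | If service and specialism were used |
|---|---|---|
| Protocol, Randomisation | correct | wrong |
| Protocol, Intervention; SAP, Introduction and Design overview | wrong | correct |
| Protocol staff model (baseline, service) | omits sex | omits specialism |
| SAP staff model (baseline, service, specialism) | omits sex; calls specialism a stratification factor when it was not | correct |

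The Protocol's model is short of one factor in both columns. The SAP's model is short only in the first.

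**2. Can the documents settle it?** Table 1 of the Protocol gives one stratification list (service, sex, age group). That is the young people's list, so it says nothing about staff. The Protocol version history records only the addition of Children's Services. The SAP history gives no reason for any change. The SAP's sample size section speaks of 35 staff randomised to control and 36 to training, so it appears to have been written after allocation. That favours specialism, as does the count of statements. Neither is confirmation.

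**3. Size of the effect on the staff tests**

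No figure in the plan bears on this, so there is none to reproduce. Inputs:

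- Staff: 35 + 36 = 71 (SAP), taken as 70 for an even split.
- Share of variance explained by the omitted factor, R²: not in the documents. Assumed 5%, 10% and 20% of the variance left after the other covariates.
- The factor is binary, splits staff in half, and is balanced almost exactly between arms.

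With the factor balanced, the true variance of the arm difference is proportional to 1 − R², while a model without the factor estimates it as proportional to 1. The standard error is therefore too large by 1/√(1 − R²), and the actual size of the nominal 5% test is approximately

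P(|Z| > 1.96/√(1 − R²)).

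| R² | SE inflation | Effective cut-off | Size by formula | Size by simulation, factor omitted | Factor included |
|---|---|---|---|---|---|
| 5% | 1.026 | 2.011 | 4.4% | 4.3% | 5.2% |
| 10% | 1.054 | 2.066 | 3.9% | 3.8% | 4.9% |
| 20% | 1.118 | 2.191 | 2.8% | 3.0% | 5.2% |

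The simulation used 70 staff and 20,000 runs per setting, with allocation balanced within the two levels of the factor. Formula and simulation agree closely. Including the factor brings the size back to about 5%. Because the factor is balanced by design, omitting it does not shift the expected arm difference.

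**The case against.** The strongest reply is that this is a slip in one sentence. Every statement of the staff factors other than the one in the Protocol's Randomisation section points to specialism. The Protocol defers analysis detail to the SAP. On that reading the SAP's allocation rule, balance check and staff model agree with one another, and the Protocol's Objective 3 text is only a shorter summary. This largely stands, and it is why the point is minor. It does not remove the need to correct the Protocol, nor does it establish which factors were entered.

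A reader might go further and make three inferences that the documents do not support.

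- *Specialists are unbalanced between arms, so the young-person comparison is partly specialist against generic.* The documents give neither the number of specialists nor the size of each service's staff. Staff were still randomised, so any imbalance would be by chance. Minimisation usually balances overall totals rather than cells within each service, so uneven splits within a service could occur under either rule. The SAP also says that a variable with a large imbalance will be added to the model.
- *The primary model should therefore adjust for practitioner specialism.* Services choose the practitioner after the young person is randomised, so this would condition on a post-randomisation variable. The reason given for the young people's strata, "as some workers specialise in working with older or younger males and females", concerns age and sex, and the primary model already adjusts for both. No text equates that with the SAP's specialist and generic categories.
- *Checking staff balance on specialism is wrong if it was not a minimisation factor.* Tabulating such a factor is an ordinary use of a baseline table.

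**Conclusion.** The point holds as a minor inconsistency. The staff minimisation factors are stated two ways and nothing reconciles them. Specialism is the likelier rule but is unconfirmed. The Protocol's staff model omits a minimisation factor whichever rule was used; the SAP's omits sex only if the Protocol's Randomisation section was followed.

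The consequence is conservative inference on secondary staff outcomes: about 4.3% to 3.0% actual size for a nominal 5% test. That range rests on the assumed 5% to 20% of variance explained and on near-exact balance. A factor that explains little would have a negligible effect. The staff estimates are not biased, and the documents give no ground for extending the point to the primary outcome.

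**What to change.** 1. Read the factors from the randomisation service's staff set-up. State them in the same words in the Protocol (Intervention and Randomisation) and in the SAP (Introduction and Design overview).
2. Specify that any second wave of staff randomisation uses the same rule.
3. In the Protocol (Analysis, Objective 3) and the SAP (Secondary outcome analysis), adjust every staff model for the baseline value plus all minimisation factors actually used. This means adding sex if the Protocol's Randomisation section was followed, and adding specialism to the Protocol's model if it was not.
4. Keep specialist versus generic staff by arm in the SAP's balance table on either reading.

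The cost is wording in both documents and about one degree of freedom in a staff sample of about 71. The SAP already uses specialism in its staff model and balance check, so it should be available, although the staff baseline lists do not name it.

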## **Participants**

Staff are considered eligible to participate in the study, and are allocated to training or business as usual, if they work with the target population within their service and volunteer and provide consent to randomisation. New staff will only be able to participate if a second wave of training is planned.

To maximise the generalisability of the study, inclusion and exclusion criteria have been minimised. All young people aged 10-21 years inclusive, referred for assessment and

intervention, to one of the participating services (only the Bridgend Youth Development Service includes participants aged 18 to 21 years), who are able and willing to consent will be eligible for inclusion in the study. Participants who have previously been randomised in the study will be excluded from further randomisation but will be maintained as part of their previously allocated group. Young people and their carers will be provided with a comprehensive information sheet prior to their initial appointment with the service. At the first appointment staff will answer any questions the parent or young person may have and if they are able and willing to consent, they will take signed consent. It is practice within all the services to request formal signed consent from family or caregivers for all young people aged 15 years or less, if parental/ caregiver consent is not forthcoming for those aged less than 15 years, staff are trained in assessing Gillick competence and making informed decisions regarding the young person's ability to consent. If a young person is considered Gillick competent consent will be sought from them directly.

After consent has been taken the staff member will collect demographic and contact data and the baseline outcomes. All young people will be identified using a unique identifier provided by the service, to ensure participants can be tracked across services and can only be randomised once. Once the baseline questionnaire is complete it will be sent using a secure, encrypted email service to research staff at the University of Kent who will use the information to conduct a randomisation using the secure randomisation service, and the outcome of the randomisation will be emailed back to the staff member on the same day. Allocation to specific staff in the control group for those in Youth Justice Services will take account of the fact that some existing staff are trained in RBT, so control group participants will only be allocated to untrained staff in this service.

After randomisation, staff will carry out the trauma screening assessment with those allocated to the intervention group and assign them to an appropriate tier of intervention support. A researcher will also contact the young person and/ or their caregiver in both control and intervention groups to explain who they are, check contact details for sending a £20 voucher redeemable at Amazon and give the young person and caregiver an opportunity to ask any questions or seek clarification about the trial. The researcher will contact the young person 3- and 9-months after randomisation to check contact details and 6- and 12- months after randomisation to conduct follow-up assessments, where they will also receive a £20 voucher. Young people will be supported in the completion of follow-up questionnaires with the researcher being concurrently available to address any issues.

